4.2 METHOD OF TREATMENT ASSIGNMENT AND BLINDING

This is an open-label single-arm study. Patients who meet all of the inclusion criteria and none of the exclusion criteria as assessed during the screening period will be enrolled in the study to receive treatment with atezolizumab.

The screening tests and evaluations will be performed within 28 days prior to Cycle 1, Day 1. Results of standard-of-care tests or examinations performed prior to obtaining informed consent and within 28 days prior to Cycle 1, Day 1 may be used; such tests do not need to be repeated for screening.

After written informed consent has been obtained and eligibility has been established, the study site will obtain the patient's unique identification number by registering the patient in an interactive voice/Web response system (IxRS) on the day of enrollment.

Patients should receive their first dose of study drug on the day of enrollment if possible. If this is not possible, the first dose should occur within 5 business days after the patient is registered in the IxRS.

4.3 STUDY TREATMENT

The investigational medicinal product (IMP) for this study is atezolizumab.

4.3.1 Formulation, Packaging, and Handling

Atezolizumab (MPDL3280A) will be supplied by the Sponsor in a single-use, 20-mL USP/European Pharmacopoeia Type 1 glass vial as a colorless to slightly yellow, sterile, preservative-free clear liquid solution intended for IV administration. The vial is designed to deliver 20 mL (1200 mg) atezolizumab solution but may contain more than the stated volume to enable delivery of the entire 20 mL volume. For information on the formulation and handling of atezolizumab, see the Atezolizumab Pharmacy Manual and Investigator's Brochure.

4.3.2 Dosage, Administration, and Compliance

The dose level of atezolizumab proposed to be tested in this study is 1200 mg (equivalent to an average body weight–based dose of 15 mg/kg) administered by IV infusion every 21 (± 3) days.

Administration of atezolizumab will be performed in a setting with emergency medical facilities and staff who are trained to monitor for and respond to medical emergencies.

The initial dose of atezolizumab will be delivered via IV infusion over 60 (± 15) minutes. If the first infusion is tolerated without infusion-associated adverse events, the second infusion may be delivered over 30 (± 10) minutes. If the 30-minute infusion is well tolerated, all subsequent infusions may be delivered over 30 (± 10) minutes. For all infusions, vital signs will be assessed per the local standard of care (see [Appendix 1](#)).

Dose modifications to atezolizumab are not permitted.

No premedication will be allowed for the first dose of atezolizumab. Premedication may be administered for Cycles ≥ 2 at the discretion of the treating physician. The management of infusion-related reactions will be according to severity as follows:

- In the event that a patient experiences a mild (NCI CTCAE Grade 1) infusion-related event, the infusion rate should be reduced to one-half the rate being given at the time of event onset. Once the event has resolved, the investigator should continue to deliver the infusion at the reduced rate for 30 minutes. If tolerated, the infusion rate may then be increased to the original rate.
- In the event that a patient experiences a moderate infusion-related event (NCI CTCAE Grade 2) or flushing, fever, or throat pain, the patient should have his or her infusion immediately interrupted and should receive aggressive symptomatic treatment. The infusion should be restarted only after the symptoms have adequately resolved to the baseline grade. The infusion rate at restart should be one-half of the rate that was in progress at the time of the onset of the infusion-related event.
- For severe or life-threatening infusion-related events (NCI CTCAE Grade 3 or 4), the infusion should be stopped immediately, and aggressive resuscitation and supportive measures should be initiated. Patients experiencing severe or

life-threatening infusion-related events will not receive further infusion and will be further managed as clinically indicated until the event resolves.

See [Appendix 5](#) for anaphylaxis precautions.

Atezolizumab infusions will be administered per the instructions outlined in [Table 4](#).

Table 4 Administration of First and Subsequent Infusions of Atezolizumab

First Infusion	Subsequent Infusions

 • No premedication administered for atezolizumab specifically is permitted • Record patient’s vital signs (heart rate, respiratory rate, blood pressure, and temperature) within 60 minutes before starting infusion. • Infuse atezolizumab (1200 mg in a 250-mL 0.9% NaCl intravenous infusion bag) over 60 (\pm 15) minutes. • If clinically indicated, record patient’s vital signs (heart rate, respiratory rate, blood pressure, and temperature) during the infusion at 15, 30, 45, and 60 minutes (\pm 5-minute windows are allowed for all timepoints). • Record patient’s vital signs (heart rate, respiratory rate, blood pressure, and temperature) at 30 (\pm 10) minutes after the infusion. • Patients will be informed about the possibility of delayed post-infusion symptoms and instructed to contact their study physician if they develop such symptoms. 	
 • If patient experienced infusion-related reaction during any previous infusion, premedication with antihistamines may be administered for Cycles \geq 2 at the discretion of the treating physician. • Record patient’s vital signs (heart rate, respiratory rate, blood pressure, and temperature) within 60 minutes before starting infusion. • If the patient tolerated the first infusion well without infusion-associated adverse events, the second infusion may be delivered over 30 (\pm 10) minutes. • If no reaction occurs, subsequent infusions may be delivered over 30 (\pm 10) minutes. Continue to record vital signs within 60 minutes before starting infusion and during and after the infusion, if clinically indicated. • If the patient had an infusion-related reaction during the previous infusion, the subsequent infusion must be delivered over 60 (\pm 15) minutes. Record patient’s vital signs (heart rate, respiratory rate, blood pressure, and temperature) every 15 (\pm 5) minutes during the infusion if clinically indicated or patient experienced symptoms during the previous infusion. • Record patient’s vital signs (heart rate, respiratory rate, blood pressure, and temperature) 30 min (\pm 10 min) after the infusion if clinically indicated or patient experienced symptoms during previous infusion.

NaCl=sodium chloride.

Guidelines for treatment interruption or discontinuation are provided in [Section 5.1.2](#).

Any overdose or incorrect administration of study drug should be noted on the Study Drug Administration electronic Case Report Form (eCRF). Adverse events associated with an overdose or incorrect administration of study drug should be recorded on the Adverse Event eCRF.

Refer to the Pharmacy Manual for detailed instructions on drug preparation, storage, and administration.

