APPENDIX 8 Management of Atezolizumab-Specific Adverse Events (cont.)

INFUSION-RELATED REACTIONS

No premedication is indicated for the administration of Cycle 1 of atezolizumab. However, patients who experience an infusion-related reaction (IRR) with Cycle 1 of atezolizumab may receive premedication with antihistamines or antipyretics/analgesics (e.g., acetaminophen) for subsequent infusions. Metamizole (dipyrone) is prohibited in treating atezolizumab-associated IRRs because of its potential for causing agranulocytosis.

Guidelines for medical management of IRRs during Cycle 1 are provided in [Table 7](#). For subsequent cycles, IRRs should be managed according to institutional guidelines.

Table 7 Management Guidelines for Infusion-Related Reactions

Event	Management
IRR, Grade 1	
 • Reduce infusion rate to half the rate being given at the time of event onset. • After the event has resolved, the investigator should wait for 30 minutes while delivering the infusion at the reduced rate. • If the infusion is tolerated at the reduced rate for 30 minutes after symptoms have resolved, the infusion rate may be increased to the original rate.
IRR, Grade 2	
 • Interrupt atezolizumab infusion. • Administer aggressive symptomatic treatment (e.g., oral or IV antihistamine, anti-pyretic medication, glucocorticoids, epinephrine, bronchodilators, oxygen). • After symptoms have resolved to baseline, resume infusion at half the rate being given at the time of event onset. • For subsequent infusions, consider administration of oral premedication with antihistamines, anti-pyretics, and/or analgesics and monitor closely for IRRs.
IRR, Grade 3 or 4	
 • Stop infusion. • Administer aggressive symptomatic treatment (e.g., oral or IV antihistamine, anti-pyretic, glucocorticoids, epinephrine, bronchodilators, oxygen). • Permanently discontinue atezolizumab and contact Medical Monitor.^a

IRR=infusion-related reaction.

^a Resumption of atezolizumab may be considered in patients who are deriving benefit and have fully recovered from the immune-related event. Patients can be re-challenged with atezolizumab only after approval has been documented by both the investigator (or an appropriate delegate) and the Medical Monitor.

APPENDIX 8

Management of Atezolizumab-Specific Adverse Events (cont.)

PANCREATIC EVENTS

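### After a Grade 3–4 infusion reaction, Protocol Section 4.3.2 and Appendix 8 disagree on which cycles the rule covers and on whether treatment may ever resume

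*Protocol*

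**What the plan says.** Protocol Section 4.3.2 introduces its rules with "The management of infusion-related reactions will be according to severity as follows" and then lists actions by CTCAE grade. For Grades 3 and 4 the infusion is stopped at once, and patients with severe or "life-threatening infusion-related events will not receive further infusion and will be" managed from then on as their condition requires, until the event is over. No cycle is named and no exception is given. The text just before the list deals with premedication at the first dose and from Cycle 2 onward, so the passage is about first and later infusions alike.

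Appendix 8, under Infusion-Related Reactions, presents Table 7 as guidance for Cycle 1 and then adds: "For subsequent cycles, IRRs should be managed according to institutional guidelines". The Grade 3 or 4 row of Table 7 tells the site to stop the infusion, treat symptoms and "Permanently discontinue atezolizumab and contact Medical Monitor". Footnote a hangs on that last instruction: "Resumption of atezolizumab may be considered in patients who are deriving benefit and have fully recovered from the immune-related event". It continues: "Patients can be re-challenged with atezolizumab only after approval has been documented by both the investigator (or an appropriate delegate) and the Medical Monitor". The opening text of Appendix 8 gives the same route in general terms for any patient who has met criteria for permanent discontinuation.

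Both texts are in force. Section 4.3.2 sends the reader to Section 5.1.2 for interruption and discontinuation, and Section 5.1.2 sends the reader to the Investigator's Brochure and Appendix 8.

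**The concern.** A site facing a severe or life-threatening infusion reaction needs one instruction. After Cycle 1 it finds a protocol rule in the main text and a referral to its own institution's practice in the appendix, in a study planned for about 25 to 30 sites. For a Cycle 1 reaction it finds the same default in both places, but only the appendix offers a way back to treatment.

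What is at stake is safety conduct. These events are severe by definition, and infusion-reaction syndromes are among the events that Section 5.2.3 requires to be reported immediately. There is also a compliance question. Section 9.2 does not allow prospective requests to deviate from the protocol, so if a re-challenge were approved under Appendix 8, a monitor could not tell from the documents whether it was permitted care or a departure from Section 4.3.2.

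**Working it through.** No arithmetic underlies the point, and the plan states no figure to reproduce. The check sets the two texts side by side.

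| Question | Section 4.3.2 | Appendix 8 |
|---|---|---|
| Which cycles are covered? | No limit; grade alone decides | Table 7 for Cycle 1; institutional guidelines afterwards |
| Grade 3–4 in Cycle 1 | Stop; no further infusion | Stop; discontinue permanently |
| Grade 3–4 in a later cycle | Same rule as in Cycle 1 | No protocol rule; institutional guidelines |
| Exception | None stated | Footnote a: benefit, full recovery and approval by both investigator and Medical Monitor |

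**Cycle scope.** The first and third rows cannot both be followed as written. Section 4.3.2 applies its rule to a Cycle 5 reaction just as to a Cycle 1 reaction, while Appendix 8 hands the Cycle 5 reaction to the institution. Some institutional guidelines may lead to the same action, but the protocol does not ensure it. The later-cycle period is most of the exposure of a patient who stays on treatment: with the cap of 32 cycles, 32 − 1 = 31 of 32 infusions fall after Cycle 1. That is a share of infusions. The documents do not say how reactions are spread over cycles.

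**Exception.** For Cycle 1 the defaults agree. The texts part only where the patient is benefiting, has recovered fully and has both approvals on record. In that case Appendix 8 lets treatment resume and Section 4.3.2 does not.

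**Reach of the footnote.** Footnote a requires recovery from an immune-related event. The same sentence appears under the other management tables of Appendix 8, so it may have been carried over. It is nevertheless attached to the infusion-reaction row. A reader cannot tell whether the exception is meant for these reactions.

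**Other places that might settle it.**

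- Section 4.6.2 lists reasons for mandatory discontinuation, including intolerable drug-related toxicity, but has no specific item for Grade 3–4 infusion reactions.
- Section 5.1.2 allows suspension for toxicity and points onward without ranking the texts.
- Table 4 says how the next infusion is to be given after a reaction, without naming a grade, so it does not itself exclude Grade 3–4.

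None of these says which text governs.

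**The case against.** The strongest reply is that this is a rule with a controlled exception. Both texts end treatment by default, Section 4.3.2 itself leads to Appendix 8, and the appendix requires two recorded approvals before any re-challenge. A reader might infer that Appendix 8 leaves re-challenge open to the site, or that the outcome depends simply on the page read. The documents do not support that: the default in Table 7 is permanent discontinuation, and no site can use footnote a on its own authority. This part of the reply stands and narrows the point. It does not remove it, because Section 4.3.2 mentions no approval route and the reply does not touch the cycle limit.

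A second reply is that the bar in Section 4.3.2 concerns only the infusion in progress, since the sentence goes on to speak of management until the event resolves. This is arguable but weak, because the preceding sentence already stops that infusion. If accepted, it would leave Section 4.3.2 silent on later doses and remove the exception conflict, but not the difference in cycle scope.

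A third reply is that footnote a has little practical reach in Cycle 1, because the first scheduled post-baseline scan is at 6 weeks and benefit would be hard to show after a reaction to the first dose. This has force, although the footnote does not tie benefit to a scan.

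A reader might also infer that discontinuations would be recorded inconsistently. That is not shown. Section 4.6.2 requires the primary reason for stopping study drug on the eCRF whichever rule is followed, and Section 5.3.5.1 sets one way of recording infusion reactions.

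**Conclusion.** The point holds as an internal inconsistency in a safety rule, in two parts. The firmer part is cycle scope: after Cycle 1 the main text fixes the action and the appendix defers to institutional practice. The narrower part is the exception: Section 4.3.2 has none, while Appendix 8 has a conditional one whose application to infusion reactions is unclear.

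It would be too strong to say that every Grade 3–4 infusion reaction is affected. In Cycle 1 the texts conflict only where all the conditions for resumption are met. After Cycle 1 they differ in scope, but what is actually done may still coincide. The number of cases is not given and is probably small. No endpoint, analysis population, power or sample size figure depends on this. It merits correction because each case may be life-threatening and the remedy is simple.

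The conclusion assumes that the bar on further infusion refers to later doses, which is the more natural reading. The cycle-scope part does not need that assumption.

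**What to change.** Reconcile Section 4.3.2, the opening resumption text of Appendix 8, and the Infusion-Related Reactions part of Appendix 8 (Table 7, its Cycle 1 limit and footnote a), so that one stated rule covers Grade 3–4 infusion reactions in all cycles. The text should say explicitly whether the resumption exception applies to infusion reactions. If it does, the footnote wording should refer to them and Section 4.3.2 should point to it; if it does not, the footnote should come off that row. Check that Table 4's instruction for the infusion after a reaction fits the chosen rule. Add a sentence stating which text governs if any difference remains. Which clinical rule to adopt is for the sponsor to decide. The cost is wording in an amendment, with no change to the statistical plan.

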4.3.3 Investigational Medicinal Product Accountability

All IMPs required for completion of this study (atezolizumab) will be provided by the Sponsor where required by local health authority regulations. The study site will acknowledge receipt of IMPs by using the IxRS to confirm the shipment condition and content. Any damaged shipments will be replaced.

IMPs either will be disposed of at the study site according to the study site's institutional standard operating procedure or will be returned to the Sponsor with the appropriate documentation. The site's method of IMP destruction must be agreed to by the Sponsor. The site must obtain written authorization from the Sponsor before any IMP is destroyed, and IMP destruction must be documented on the appropriate form.

Accurate records of all IMPs received at, dispensed from, returned to, and disposed of by the study site should be recorded on the Drug Inventory Log.

4.3.4 Post-Trial Access to Atezolizumab

The Sponsor will evaluate the appropriateness of continuing to provide atezolizumab to patients who are still on therapy at the end of study. Decisions will be made in accordance with the Roche Global Policy on Continued Access to Investigational Medicinal Product, available at the following Web site:

http://www.roche.com/policy_continued_access_to_investigational_medicines.pdf

4.4 CONCOMITANT THERAPY

Concomitant therapy includes any medication (e.g., prescription drugs, over-the-counter drugs, vaccines, herbal or homeopathic remedies, and nutritional supplements) used by a patient from 7 days prior to screening until the study completion/discontinuation visit. All such medications should be reported to the investigator and recorded on the Concomitant Medications eCRF.

4.4.1 Permitted Therapy

Premedication with antihistamines may be administered for any atezolizumab infusions after Cycle 1.

Patients should continue use of maintenance therapy as follows:

- Hormonal therapy with gonadotropin-releasing hormone agonists or antagonists for prostate cancer
- Oral contraceptives
- Hormone-replacement therapy
- Prophylactic or therapeutic anticoagulation therapy (such as low-molecular-weight heparin or warfarin at a stable dose level)
- Palliative radiotherapy (e.g., treatment of known bony metastases), provided it does not interfere with the assessment of tumor target lesions (e.g., the lesion being irradiated is not the only site of disease, because that would render the patient not evaluable for response by tumor assessments according to RECIST v1.1)
 - It is not a requirement to withhold atezolizumab during palliative radiotherapy
- Inactive vaccinations, but not live, attenuated vaccinations, are permitted during the course of the study (i.e., only inactivated forms of the Influenza vaccinations are permitted). Live, attenuated vaccinations are prohibited (see Section 4.4.3).
- Megestrol administered as an appetite stimulant
- Inhaled corticosteroids for chronic obstructive pulmonary disease
- Mineralocorticoids (e.g., fludrocortisone)
- Low-dose corticosteroids for patients with orthostatic hypotension or adrenocortical insufficiency

In general, investigators should manage a patient's care with supportive therapies as clinically indicated per local standards. Patients who experience infusion-associated symptoms may be treated symptomatically with acetaminophen, ibuprofen, diphenhydramine, and/or famotidine or another H₂-receptor antagonist per standard practice. Serious infusion-associated events manifested by dyspnea, hypotension, wheezing, bronchospasm, tachycardia, reduced oxygen saturation, or respiratory distress should be managed with supportive therapies as clinically indicated (e.g., supplemental oxygen and β_2 -adrenergic agonists) see [Appendix 5](#).

All medications must be recorded on the appropriate Concomitant Medications eCRF.

4.4.2 Cautionary Therapy for Atezolizumab-Treated Patients

Systemic corticosteroids and TNF- α inhibitors may attenuate potential beneficial immunologic effects of treatment with atezolizumab. Therefore, in situations in which systemic corticosteroids or TNF- α inhibitors would be routinely administered, alternatives, including antihistamines, should be considered first by the treating physician. If the alternatives are not feasible, systemic corticosteroids and TNF- α inhibitors may be administered at the discretion of the treating physician except in the case of patients for whom CT scans with contrast are contraindicated (i.e., patients with contrast allergy or impaired renal clearance) (see also Section 4.4.1).

Systemic corticosteroids are recommended, with caution at the discretion of the treating physician, for the treatment of specific adverse events when associated with atezolizumab therapy. Guidelines for the management of immune-mediated adverse events are described in the Investigator's Brochure.

The concomitant use of herbal therapies is not recommended because their pharmacokinetics, safety profiles, and potential drug-drug interactions are generally unknown. Their use for patients on this study is allowed at the discretion of the investigator, however the herbal therapy must have no known interactions with any study treatment nor can it be used specifically for the treatment of cancer (see Section 4.4.3).

4.4.3 Prohibited Therapy

Any concomitant therapy intended for the treatment of cancer, whether health authority-approved or experimental, is prohibited for various time periods prior to starting study drug, depending on the anti-cancer agent (see Section 4.1.2), and during study drug treatment until disease progression is documented and the patient has discontinued study drug. This includes but is not limited to chemotherapy, hormonal therapy, immunotherapy, radiotherapy, investigational agents, or herbal therapy (unless otherwise noted).

The following medications are prohibited while in the study, unless otherwise noted:

- Traditional herbal medicines intended for the treatment of cancer or those with known interactions with the study treatment, because their use may result in unanticipated drug-drug interactions that may cause or confound assessment of toxicity
- Any live, attenuated vaccine (e.g., FluMist®) within 4 weeks prior to Cycle 1, Day 1, at any time during the study, or for 5 months after the last dose of atezolizumab
- Use of corticosteroids to premedicate patients for whom CT scans with contrast are contraindicated (i.e., patients with contrast allergy or impaired renal clearance); in such patients, non-contrast CT scans of the chest and non-contrast CT scans or MRIs of the abdomen and pelvis should be performed.

